#### 3.2 Randomization

The trial used a centralized interactive web response system (IWRS) to perform patient allocation (CleanWeb software, Telemedecine Technologies, Boulogne-Billancourt, France). The data manager for the study prepared the randomization schedule for each clinical site participating in the trial. The randomization schedule has the following characteristics: 1. Stratified by center; 2. blocks of size four with equal numbers of patients assigned to the early-TIPS or glue obliteration within each block. The block size was only known by the senior statistician and the data manager of the study.

Only study-certified clinic staff with individually assigned userid/password can access the randomization application. Only participants meeting the inclusion/exclusion criteria according to data entered in the eCRF

system, are listed among the participant IDs eligible for randomization. The date and time of the completion

of the randomization treatment assignment is the time of study entry for each patient.

## 3.3 Sample size

The sample size is calculated with a projected rate of composite event of failure at 12 months of 15% in the group "TIPS" [estimated from Garcia Pagan, New Engl J Med 2010] versus 40% in the group « glue» [estimated from Hou, Gastrointest Endosc 2009].

A number of 52 patients in each group will achieve 80% power to detect TIPS superiority using a one-sided logrank test at a 0,050 significance level, with a proportion dropping out of both groups of 10%.

Total number of scheduled patients recruited or observations collected: 104.

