## **Section 4: Statistical Principles**

#### 4.1 Confidence Intervals and P-values

All tests will be two-sided, with p values of less than 0.05 denoting statistical significance. 95% confidence interval will be used to report effect estimates of secondary endpoints.

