## **Primary composite endpoint**

The Kaplan Meier method will be used to estimate rate of composite event over the 12-month follow-up. The composite event rates will be compared between study arms using the log-rank test. Hazard ratio for composite event rate (TIPS vs. GO) and its 95% confidence interval will be determined using a Cox proportional hazard model. In this model, a center effect will be tested as well as interaction between treatment and center. The assumption of proportional hazards will be tested using Schoenfeld residuals and if violated, the model will be fitted with a treatment-time interaction or a time-varying covariate, as appropriate.

The composite event rate at 12 months will be described according to a number of covariates including age, gender, and specific liver scores (Child-Pugh and MELD) to examine their potential effects. Each of these factors will be analyzed statistically using a Cox proportional hazard model incorporating terms for treatment strategy, the covariate and the strategy-by covariate interaction. The number of patients with composite event, estimated hazard ratios, and associated 95% confidence intervals will be calculated within each of the subgroups generated by these analyses.

Covariate			Treatment effect	P
	n	No. Events	HR - 95%CI	value
Intervention				р
Glue			Ref	
obliteration				
Early			Treatment effect	
TIPS				
Subgroup analyses				
Age				P*
<median< td="">		<median effect<="" td="">	</median>	</median<>			<median effect<="" td="">	</median>	

>median			>median effect	
Sex				P*
Male			Effect in men	
Female			Effect in women	
Child Pugh				P*
score				
В			Effect in B patients	
С			Effect in C patients	
MELD				P*
<median< td="">		<median effect<="" td="">	</median>	</median<>			<median effect<="" td="">	</median>	
>median			>median effect	
EH upon adm	niss	on		
No				
Yes				
High risk pat	ient	s (Child-Pugh	C, or Child-Pugh B with active bleeding)	
Not high			Effect in not high-risk patients	
risk				
High risk			Effect in high-risk patients	
Shock				P*
No shock			Effect in patients with shock	
Shock			Effect in patients without shock	
ACLF upon a	adm	ission†		P*
Grade 1				_
Grade 2				_
Grade 3				
Red blood cell transfusion during initial hospitalization				P*
0	)		Effect in untransfused patients	
1-2			Effect in transfused patients 1-2 RBC units	
>2			Effect in transfused patients with more than RBC units	

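### The sample size assumes a one-sided 0.05 log-rank test, but the SAP makes all tests two-sided at 0.05, and the stated 80% power does not belong to the one-sided test

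*SAP*

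**What the plan says.** Section 3.3 (Sample size) gives the planning assumptions: a "projected rate of composite event of failure at 12 months of 15% in the group" assigned to TIPS, "versus 40% in the group" assigned to glue, and 10% dropout in both groups. It concludes that "52 patients in each group will achieve 80% power to detect TIPS superiority using a one-sided logrank test at a 0,050 significance level", for a total of 104.

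Section 4.1 (Confidence Intervals and P-values) sets the general rule: "All tests will be two-sided, with p values of less than 0.05 denoting statistical significance". It makes no exception for the primary endpoint.

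Section 6.2 (Primary composite endpoint) says "The composite event rates will be compared between study arms using the log-rank test" and gives no side. It reports the hazard ratio with a 95% confidence interval, which matches a two-sided 0.05 test.

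Section 3.1 (Trial Design) gives 1:1 allocation and 12 months of follow-up.

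**The concern.** There are two linked problems.

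First, the success criterion for the primary endpoint is fixed in two ways. Under 3.3 TIPS is superior if z passes 1.645; under 4.1 it must pass 1.96. Used as the decision rule, the 3.3 version doubles the chance of falsely declaring TIPS superior, from 2.5% to 5%. The trial is open label, so a threshold left unsettled until the results are known invites a choice made in their light.

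Second, the 80% power and the 52 per group should follow from the test named beside them. If they do not, either the test or the power in 3.3 is misstated, and a reader cannot tell which test the trial was sized for.

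**Working it through.** **Inputs.** From 3.3: 12-month event rates 0.15 and 0.40, 52 per group (104 in total), 10% dropout, 80% power, one-sided alpha 0.05. From 4.1: two-sided alpha 0.05. From 3.1: 1:1 allocation and 12 months of follow-up. Assumptions, because the SAP names neither a formula nor a dropout model: exponential survival, and dropout either as a 10% outright loss of patients or as exponential censoring reaching 10% at 12 months.

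**Step 1. Effect size.** HR = ln(0.85)/ln(0.60) = 0.1625/0.5108 = 0.318, so |ln HR| = 1.145. The mean event probability is (0.15 + 0.40)/2 = 0.275.

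**Step 2. Try to reproduce 52 per group at 80% power.** The z value for 80% power is 0.842. The z value for alpha is 1.645 one-sided and 1.960 two-sided.

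- Schoenfeld: events = 4(z_α + z_β)² / (ln HR)²
- Freedman: events = (z_α + z_β)² × [(1 + HR)/(1 − HR)]²
- Total N = events / 0.275 / 0.9

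| Test | Method | Events | Total N incl. dropout |
|---|---|---|---|
| One-sided 0.05 | Schoenfeld | 18.9 | 76.2 |
| One-sided 0.05 | Freedman | 23.1 | 93.4 |
| Two-sided 0.05 | Schoenfeld | 23.9 | 96.7 |
| Two-sided 0.05 | Freedman | 29.3 | 118.5 |

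The one-sided test needs about 77 to 94 patients, not 104. The planned 104 falls inside the two-sided range. The Lakatos method, which builds the 10% exponential dropout into the calculation, gives 40.9 per group one-sided and 51.9 per group two-sided.

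**Step 3. Power of the planned trial.** With 10% lost outright, 104 × 0.9 = 93.6 evaluable patients and 93.6 × 0.275 = 25.7 events.

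- Schoenfeld: Φ(√25.7 × 1.145/2 − z_α) = Φ(2.905 − z_α), which is 90% one-sided and 83% two-sided.
- Freedman: Φ(√25.7 × (1 − 0.318)/(1 + 0.318) − z_α) = Φ(2.624 − z_α), which is 84% one-sided and 75% two-sided.

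With exponential dropout the expected events are 52 × (0.1426 + 0.3813) = 27.2.

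| Method | One-sided 0.05 | Two-sided 0.05 |
|---|---|---|
| Simulated log-rank, 52 per group, exponential dropout (20,000 trials) | 89.0% | 81.2% |
| Simulated log-rank, 47 per group (10% lost outright) | 87% to 88% | 79% to 80% |
| Lakatos, 52 per group, exponential dropout | 87.7% | 80.1% |
| Schoenfeld, 10% lost / exponential dropout | 90% / 91% | 83% / 85% |
| Freedman, 10% lost / exponential dropout | 84% / 85% | 75% / 77% |

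No log-rank method gives 80% for the one-sided test. The two-sided values lie around 80%.

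**Step 4. How often the two rules would disagree.** At the design effect, 89.0% − 81.2% = 7.8% of trials, about one in thirteen, would succeed under 3.3 and fail under 4.1. With no treatment difference the figure is 5% − 2.5% = 2.5%.

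**The case against.** The strongest reply is that 3.3 only records planning, while 4.1 sits under Statistical Principles, covers all tests and governs the analysis. On that reading a one-sided p of 0.03 is plainly not a success, and the extra false-positive risk arises only if the analyst departs from 4.1. This is the more natural reading, and it supports aligning 3.3 with 4.1. It does not remove the fault: nothing in the SAP says 4.1 overrides 3.3, and 3.3 would still attach its power to a test that will not be used.

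A second reply is that the origin of 52 cannot be established. The two-sided unpooled two-proportion formula gives 46.15/0.9 = 51.3, hence 52; the one-sided pooled formula with continuity correction gives 46.04/0.9 = 51.15, also 52. This stands as a caution about what the sponsor calculated. Neither is a log-rank test, though, so neither rescues the statement in 3.3.

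A third reply is that a real one-sided log-rank calculation could give about 80% if follow-up were spread over 6 to 12 months (81% one-sided, 71% two-sided by simulation). That contradicts the 12 months of follow-up in section 3.1.

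Finally, the practical effect is limited: no patients are added and the two-sided test keeps about 80% power. That is correct. It makes the repair easy but does not make it unnecessary.

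**Conclusion.** The concern holds. Sections 3.3 and 4.1 set different thresholds for the primary test and section 6.2 does not settle which applies. The 80% in 3.3 is not the power of the one-sided 0.05 log-rank test named there, which is about 88% to 89% (84% to 91% across methods). It agrees with the two-sided test in 4.1, at about 80% to 81% (75% to 85% across methods).

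This should not be read as a claim that the trial is underpowered: most methods put two-sided power near or above the target, and only the Freedman formula falls clearly below it. The figures rest on exponential survival, the planned 15% and 40%, 12 months of follow-up and the two dropout models above. The contradiction in sidedness depends on none of these. Because it concerns the success criterion of the primary endpoint, it must be corrected before the final analysis.

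**What to change.** - In 3.3, replace one-sided with two-sided and restate the power for 52 per group with 10% dropout: about 81% by simulation, or 75% to 83% by the Freedman and Schoenfeld formulas with 10% lost outright. Name the method and the dropout model.
- In 6.2, state that the primary log-rank test is two-sided at 0.05.
- Keep the total at 104.

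If the sponsor really did intend a one-sided 0.05 test, 4.1 would need an explicit and justified exception and 3.3 a corrected power of about 88% to 89%. That route carries the 5% false-positive rate in favour of TIPS and is harder to defend.

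The cost is SAP wording only, with no extra patients and no change to data collection. What is given up is any reading of the SAP that allows success on a one-sided 0.05 result.

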## 3.4 Timing of final analysis

The trial is scheduled to end with the final 12-month follow-up appointment. The data will be cleaned, verified and locked. Final analysis will begin once the principal investigator has confirmed the final database.

## **Section 4: Statistical Principles**

#### 4.1 Confidence Intervals and P-values

All tests will be two-sided, with p values of less than 0.05 denoting statistical significance. 95% confidence interval will be used to report effect estimates of secondary endpoints.

## 4.2 Adherence and protocol deviations

The list of protocol deviations will be established and the reasons for non-evaluable cases will be indicated as following:

- Inclusion criteria not satisfied.
- Deviations related to the procedure administration

## 4.3 Analysis populations

The primary analysis will be performed according to the intention-to-treat (ITT) principle.

#### **Modified intention to treat population (mITT)**

The mITT population will consist of all eligible randomized patients in the treatment group assigned by the randomization, irrespective of whether the patient underwent the procedure allocated by randomization or if crossovers occurred. Randomized patients who were later found to not meet inclusion criteria will not be included in the mITT population.

#### Per protocol population

This population will include all randomized patients with the exception of patients who could not undergo the procedure the patients were assigned to including TIPS failure. Randomized patients who were later found to not meet inclusion criteria will not be included in the per protocole population.

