#### Early TIPS procedure in experimental arm (Group A):

- TIPS using covered stent will be placed under general anesthesia and with radioscopic guidance by experts.
- The procedure should be performed as soon as possible after randomization and before Day 4.
- Portal pressure should be taken at the time of TIPS insertion, with a goal of hepatic venous pressure gradient of less than 12 mmHg at the end of the procedure.
- Embolization of collaterals will not be authorized in the present study.

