## Glue obliteration procedure in control arm (Group B):

- Filling of varice(s) with tissue adhesive under endoscopic guidance will be initially performed in all patients under general anesthesia. The use of a Doppler EUS will be at the discretion of the practitioner.
- Endoscopic control (and further glue obliteration session if necessary) will be performed in the group B between day-5 and day-8 after the initial bleeding. A new session will then be proposed at days 42+/-7, 90+/-14, 180+/-14 and 365+/-14.
- Endoscopic reports will be systematically collected. The report should specify the topography and size of varices (if possible, a picture will be collected), the type of glue, the volume injected as well as the proportion of Lipiodol.
- In the case of coexistence of esophageal varices, the latter will be systematically treated during the same endoscopic session by band ligation.
- In patients randomized to group B the decision of "salvage TIPS" will be left to the discretion of the investigator and will be then considered as a failure of the endoscopic procedure.
- When placing TIPS for another indication during follow-up in the group B, the patient will be censured at the date of installation of the device.
- In the absence of contraindication, a non-selective beta-blocker treatment will be proposed in the group B according to the recommendations of the Baveno VI Consensus Workshop 2015 (14).

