## **Section 5: Trial Population**

## **5.1 Eligibility**

**Inclusion criteria:** 

- Age  $\geq$  18 and  $\leq$  75 years.
- Cirrhotic patients with variceal bleeding from gastroesophageal gastric varices type 2 or isolated gastric varices type 1 or 2 (Sarin classification) according to the following criteria: endoscopic signs of an active spurting or oozing from gastric varices (GV); adherent blood clots, white nipple signs, or erosions on the GV and absence of other bleeding sources. Cirrhosis: The diagnosis of liver cirrhosis is based on previous liver biopsy or on the combination of clinical, biochemical, and radiological findings. If biopsy findings are unavailable and in case of non-complicated cirrhosis, non-invasive markers will be used.
- Hemodynamically stable patient without clinically significant rebleeding (Baveno criteria) within 12 hours after the initial endoscopy with glue obliteration.
- Written informed consent obtained.
- Patient affiliated to a social security system.

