## **6.2 Analysis Methods**

Analyses of all endpoints will be performed on the mITT as well as the per protocol population unless specified.

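### The per-protocol set excludes TIPS failures and patients who could not receive TIPS but has no glue counterpart, so the two arms are not selected by the same rule

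*SAP*

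**What the plan says.** **Who is excluded.** SAP section 4.3 (Per protocol population) takes all randomised patients "with the exception of patients who could not undergo the procedure the patients were assigned to including TIPS failure". It also removes patients later found ineligible. Failure is named for TIPS only.

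**When each procedure happens.** For group A, section 3.1 states: "The procedure should be performed as soon as possible after randomization and before Day 4". For glue, the same section states: "Filling of varice(s) with tissue adhesive under endoscopic guidance will be initially performed in all patients under general anesthesia". The inclusion criteria in section 5.1 require a stable patient "without clinically significant rebleeding (Baveno criteria) within 12 hours after the initial endoscopy with glue obliteration", so this first glue session precedes randomisation in both arms. After it, "Endoscopic control (and further glue obliteration session if necessary) will be performed in the group B between day-5 and day-8". Salvage TIPS in group B "will be then considered as a failure of the endoscopic procedure", but it is not listed as a per-protocol exclusion.

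**How the set is used.** Section 6.2: "Analyses of all endpoints will be performed on the mITT as well as the per protocol population unless specified". Section 4.3 also says: "The primary analysis will be performed according to the intention-to-treat (ITT) principle".

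**The concern.** Entry to the per-protocol set depends on what happens after randomisation, and the dependence differs by arm. A group A patient who dies, rebleeds or deteriorates so that TIPS cannot be placed is removed together with the event. A patient in whom TIPS was tried and failed is removed too. If the first glue session counts as group B's procedure, hardly any group B patient can be unable to undergo it, so nearly all of that arm's early events stay in.

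Two other parts of the SAP make the asymmetry plain. Section 6.1 lists technical failure of glue as an outcome beside technical failure of TIPS, yet only the latter is a per-protocol exclusion. The safety population in section 4.3 keeps attempted TIPS whether or not it was completed, while the per-protocol set does the opposite.

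At stake is how the second set of results is read. Section 6.2 puts it beside the mITT results for every endpoint, including the primary one, and does not say which carries weight. Part of any agreement or gain in that set could come from who was removed.

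**Working it through.** **1. Group B under each reading of the assigned procedure**

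| Reading | Group A patients dropped | Group B patients dropped |
|---|---|---|
| Initial glue (listed first under the group B procedure) | TIPS failures; events before Day 4 that prevent TIPS | Almost none: glue already given |
| Day 5-8 session (after randomisation; glue only if needed) | Same | Patients with an event that prevents that session |

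The first reading is the more natural one, because the glue at day 5-8 is conditional. On the second, the group B window is longer than group A's. Neither reading gives the arms the same rule.

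**2. Planning inputs.** Section 3.3 gives 52 per group and 12-month failure of 15% (TIPS) and 40% (glue). A one-sided, continuity-corrected two-proportion formula gives 47 per group, and 47 × 1.1 = 51.7, so the plan's 52 is reproduced. The point does not depend on this. Expected events are 0.15 × 52 = 7.8, about 8, and 0.40 × 52 = 20.8, about 21.

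**3. Effect on the TIPS rate.** If k patients are dropped and e of them had an event, the rate becomes (8 − e)/(52 − k). It falls whenever e/k exceeds 8/52 = 15.4%. With k = 3 (assumed) and glue unchanged at 21/52 = 40.4%:

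| Events among the 3 dropped | TIPS rate | Difference from glue |
|---|---|---|
| No exclusion | 8/52 = 15.4% | 25.0 points |
| 3 | 5/49 = 10.2% | 30.2 points |
| 2 | 6/49 = 12.2% | 28.1 points |
| 1 | 7/49 = 14.3% | 26.1 points |
| 0 | 8/49 = 16.3% | 24.1 points |

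One event among the three is enough to move the result towards TIPS. With none it moves slightly the other way.

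**4. Simulation with no treatment effect.** Settings: 52 per arm, 40% failure in both arms, exclusions in the TIPS arm only (the first reading), log-rank test, 4,000 runs per setting. The shares are assumptions. Every event before TIPS is taken to prevent it.

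| Event before TIPS | TIPS failures dropped | Falsely favours TIPS, one-sided 0.05 | Mean spurious difference |
|---|---|---|---|
| 0% | none | 5.1% | 0.3 points |
| 2% | none | 7.3% | 1.1 points |
| 5% | none | 10.8% | 3.4 points |
| 10% | none | 19.3% | 6.4 points |
| 0% | 5%, same hazard | 4.9% | −0.1 points |
| 2% | 5%, doubled hazard | 9.3% | 2.4 points |
| 5% | 5%, doubled hazard | 13.6% | 4.3 points |
| 10% | 5%, doubled hazard | 24.2% | 7.7 points |

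The bias comes from dropping events and high-risk patients. Dropping failures with ordinary prognosis does nothing. The 10% rows are extreme: they need 10/40, a quarter of the year's failures, to occur before TIPS.

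**The case against.** The strongest reply is that the primary result is protected. Section 4.3 sets an intention-to-treat primary analysis, and the mITT set keeps eligible patients whatever procedure they received. This stands. A reader might infer that a favourable per-protocol result could rescue a weak primary one; formally it cannot.

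A reader might also infer that the weak points of the TIPS strategy vanish from the trial's results. They do not. Technical failure of TIPS is reported on the safety population (sections 6.1 and 6.2), and deaths and rebleeds while waiting for TIPS stay in the mITT analysis.

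Third, it is tempting to say that procedural failure removes a patient in one arm and counts as an outcome in the other. The primary endpoint in section 6.1 is death or clinically significant rebleeding only. Salvage TIPS is called an endoscopic failure in section 3.1 but is not a primary event, and section 4.3 does not say whether such patients stay in the per-protocol set.

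Fourth, the general clause is worded alike for both arms, and glue given to everyone before randomisation is an odd candidate for what group B was assigned to. On the day 5-8 reading the bias could be offset or reversed. This stands as a limit on direction, but it also confirms that the rule is undefined for group B.

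Finally, leaving untreated patients out of a per-protocol set is conventional, and the window before TIPS is short. Both are true. Neither explains why failure is an exclusion for one procedure only.

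**Conclusion.** The point holds as a defect in a non-primary analysis. The exclusion rule depends on outcomes after randomisation and is not comparable between arms. On the more natural reading it falls mainly on group A and tends to favour TIPS.

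The stronger statement, that the per-protocol result favours TIPS by construction, is not supported. The direction rests on which glue session counts as group B's procedure, and on the dropped patients having events more often than the 15.4% of their arm. A rebleed followed by successful TIPS stays in the set. Counting time from randomisation in patients who had to reach TIPS adds some immortal time, but only a few days out of 365.

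The size cannot be determined, because the SAP gives no rate of TIPS failure or of events before TIPS. With three exclusions the illustrated TIPS rate runs from 10.2% to 16.3% against 15.4%. With 52 per arm, two or three patients are enough to be visible. The change is worth making because it is cheap, not because the trial's main conclusion is at risk.

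**What to change.** In section 4.3 (Per protocol population):

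- Delete the closing reference to TIPS failure, and keep patients in whom the assigned procedure was attempted, whatever its technical success, in both arms.
- State what counts as having undergone the assigned procedure in group B, including for a patient who needed no further glue at day 5-8.
- Do not exclude patients whose procedure was prevented by death, rebleeding or deterioration after randomisation.
- Exclude, in both arms alike, only ineligible patients and those whose deviation had a non-outcome reason, such as refusal or logistics.

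In section 4.2, record that reason for each deviation; the two present categories are too broad to separate outcome-driven from other reasons. In section 6.2, label the per-protocol analysis as supportive of the ITT/mITT analysis.

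The cost is SAP wording and a classification of deviations, best settled before database lock because the trial is open label. No new patient data should be needed, provided that the reason for a missed procedure is already recorded. The downside is that the per-protocol set moves closer to mITT and its result may look slightly less favourable to TIPS.
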